### **7.2.2. Environment-level components.**

The primary environmental difference between the *STAND+* and *MOVE+* study arms will be the installation of a sit-stand workstation for the *STAND+* arm only. The workstations will be installed by our trained research staff, as well as worksite-specific ergonomic and wellness professionals. The Ergotron sit-stand workstation Workfit-TL model (Ergotron, Inc., St. Paul, MN) has been selected because it is able to be retro-fitted for use with almost all workspaces, requires little or no installation as it is simply placed on the existing desk surface, is affordable relative to many alternatives, has more desk surface area than many alternatives on the market, it can be easily raised and lowered to a broad range of positions, and can accommodate one or two large computer monitors. The Workfit-TL transitions from seated to standing positions by holding two levers and providing minimal force. Prior to installation a workspace inventory will be conducted for each participant to identify any potential barriers to use such as overhead shelving, insufficient computer cabling, or fixed keyboard trays. To eliminate these barriers, overhead shelving will be moved by worksite facilities management, cable extenders added (if needed), and additional wireless keyboards will be provided to those with keyboard trays so that participants are not required to move their existing keyboards with each sit-stand transition. The same Ergotron Workfit-TL will be installed at the 12-month time point for all *MOVE+* arm participants. All participants will receive ergonomic instructions for both sitting and standing postures via the e-newsletter and will undergo a coaching session at the time of installation.

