suggested Toolkit items will emerge. This will be discussed and documented during the quarterly meetings and quarterly audits. The required multi-level tactics show reinforcement of behavior change across the social-ecological spectrum, utilizing all aspects of the behavior change taxonomy wheel. This integrated approach shows promise for shifting the cultural norm within a workplace from reinforcing highly sedentary, seated behavior patterns to one where standing and moving is expected, rewarded, and celebrated. This cultural shift is necessary to produce sustainable, long lasting changes that are likely to impact health and well-being on a large scale.

Both *STAND+* and *MOVE+* worksites received the same multi-component intervention toolkit targeting organizational, environmental, cultural, and social changes within the workplace. Examples organizational changes included: (a) installation of sit-stand workstations (b) quarterly support emails, (c) ergonomic support and (d) bi-weekly e-newsletters. Examples of Environmental changes included: walking routes, (b) signage, (c) waste and recycling bin reallocation, (d) use of centralized printing areas, (e) inviting stairways and an (g) ideaboard. Examples of cultural and social changes included (a) allowance of 5-min breaks every hour, (b) promotion of face-to-face interaction, rather than email, (c) standing meetings, (d) walking meetings, (e) stretch breaks), (f) contests), and (g) social groups.

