### 7.3 Difference between Intervention Arms

The primary study arm differences will be implemented at the environmental level with the provision of a sit-stand desk at the start of the intervention for the *STAND+* group only. This primary difference will require small adaptations to other intervention strategies. First, participant goals will differ per arm to reflect the different arm intervention goals (i.e., increasing standing and LPA time for *STAND+* vs. increasing LPA only for *MOVE+*). All participants will be encouraged to adhere to a '30-min rule', however, the meaning of this target rule will differ per arm. For the *STAND+* group this will be communicated as achieving a 30:30-minute sit to stand ratio to ultimately replace half their sit time with a combination of standing and moving at work. For the *MOVE+* group this will be communicated as replacing 30 min of sit time with an equal accumulation of moving more throughout the work day. The 1-on-1 sessions held at the start of the program will facilitate specific goal setting at the individual level to help achieve the '30-minute rule' per arm. Consequently, the strategies communicated during the 1-on-1 session and throughout the study duration will differ slightly per arm (see Table 3).

Second, although the *STAND+* and *MOVE+* arms will be provided with an identical Stand & Move Toolkit and the same level of support to implement socio-ecological changes, it is likely that the application of the Toolkit will differ per arm to target the specific target intervention arm goals. Finally, in some instances, the e-newsletter topics will remain the same across arms but the content will be adjusted per arm to reduce contamination and ensure that information is specific to the intervention arm. For example, the ergonomically themed e-newsletter will include sit-stand desk information for the *STAND+* group, however, the *MOVE+* content will only include seated desk information. Stand & Move intervention support for *STAND+* will cease following the 12-month assessment period. However, *MOVE+* participants will receive a sit-stand desk and ergonomic advice at the 12-month time point, and after which no additional intervention

support will continue post-installation. Both arms will still have access to the Toolkit during this follow-up period (12–24 months).

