on geographical location so that we will not have any confounding by geographical location (AZ vs. MN). We will identify six pairs of sites in AZ and six pairs in MN, with the pair members having the same sector (academia, government, or healthcare/industry). Each pair will be randomized so that one worksite in each pair is assigned to the *MOVE+* intervention and the other in that pair assigned to the *STAND+* intervention. One of the site PIs and a Biostatistician at the University of Minnesota will be responsible for the randomization. Randomization will occur immediately following the baseline data collection for both sites. The PI will notify the biostatistician when there are two matched worksites ready for randomization. The two worksites will be ordered as “First” and “Second” depending on the calendar dates of the baseline data collection. The statistician, with no knowledge of the worksites, will use a coin flip to assign the two worksites to the *STAND+* or *MOVE+* interventions. Initial analyses will provide descriptions of the baseline frequencies and means (SD) of characteristics by worksite and by experimental condition. Statistical testing of differences in baseline characteristics is not necessary, but will provide assurance that the randomization has not produced a grossly unbalanced assignment. If the distributions of our outcome variables are not normally distributed, we will log-transform the outcome data. Our primary hypotheses will be tested by invoking a repeated-measures hierarchical linear model of the experimental contrast between the two conditions of the 12-month measure of LPA (min/ 8-h) and sitting (min/8-h), respectively. Because total time is standardized to 8 h, we will also express our outcomes in percent of time in LPA and sitting. A repeated measures hierarchical analysis will be conducted. The covariates expected to include are age, sex, body mass index, and the baseline values of the dependent variables (e.g., sitting time, LPA, and metabolic risk score). The resulting estimate and its standard error provide a t-statistic based on  $2(g-1)$  degrees of freedom (df), where g represents the number of worksites per experimental condition [54]. A similar analysis will examine the secondary hypothesis for the metabolic risk score. Other outcomes, including sit-stand transitions, will use hierarchical generalized linear models with a log link. The analysis approach for process (3 month) and maintenance (24 month) outcomes will be similar. In terms of missing data, sensitivity to member-dropout is small; if on average only 85% are followed, the detectable effect sizes increase by a factor 1.05. Worksite dropout would be a major threat to validity, but that is highly unlikely to occur. Baseline characteristics of those not providing follow-up data will be examined to assess whether these are non-informative missingness. Under the assumption that dropout is not related to the measures that would have been collected, the analysis of the data excluding dropouts is unbiased.

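### The 24-month maintenance analysis is set up like the 12-month arm contrast, but MOVE+ receives the same workstation at month 12, so a null 24-month contrast cannot be read as loss of effect

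*Combined protocol and SAP*

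**What the plan says.** - **Analysis (12.1).** The primary hypotheses are tested in a repeated-measures hierarchical model of the "experimental contrast between the two conditions of the 12-month measure of LPA", and likewise for sitting. For the other visits the plan says: "The analysis approach for process (3 month) and maintenance (24 month) outcomes will be similar".
- **Aim (Primary Aim).** The 24-month visit is there to measure maintenance. The term is not defined, and H1 and H2 are stated over 12 months.
- **MOVE+ at month 12 (1, 7.2.2, 7.3).** "The same Ergotron Workfit-TL will be installed at the 12-month time point for all" MOVE+ participants. Participants "will undergo a coaching session at the time of installation". Section 7.3 says MOVE+ "participants will receive a sit-stand desk and ergonomic advice at the 12-month time point, and after which no additional intervention" support continues.
- **STAND+ after month 12 (7.3).** Intervention support "will cease following the 12-month assessment period". Both arms keep access to the Toolkit until month 24.
- **What the arms shared before month 12 (7.2.3, 7.3).** Both arms' "worksites received the same multi-component intervention toolkit targeting organizational, environmental, cultural, and social changes within the workplace", with the same level of support. Section 7.3 adds that participant goals, the meaning of the 30-minute rule, the 1-on-1 strategies and some newsletter content differed by arm.

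**The concern.** At 3 and 12 months the arms differ in the workstation and in the standing-oriented goals and messages that go with it. At 24 months both arms have workstations. The contrast then compares desks from the start, with 12 months of standing-targeted support, against desks added at month 12 without such support afterwards.

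That is a legitimate randomised comparison, but it does not measure maintenance. It moves towards zero if STAND+ loses its gains and also if MOVE+ catches up. If it is the only 24-month result, a fully durable effect could be reported as having faded. Alternatively, the analyst could pick another maintenance estimate after seeing the data. If 'similar' refers only to the type of model, the second risk remains, because no section then says which quantity represents maintenance.

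**Working it through.** **1. What the contrast estimates.** Let δ be the 12-month between-arm difference in favour of STAND+, r the share of it that STAND+ retains at month 24, and u the share that MOVE+ gains after installation. If all other changes after month 12 are equal in both arms, then

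expected 24-month contrast = δ × (r − u).

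The pairs (r, u) = (1, 1), (0.5, 0.5) and (0, 0) all give zero. A larger sample does not separate them.

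**2. Standard error from the plan's own figures.** Section 12.2 gives 12 worksites per arm, 30 members per worksite, 22 df, two-sided 5% and 80% power, with detectable differences of 14.6 min/8 h (sitting) and 12.2 min/8 h (LPA). I read its formula as

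D² = (t₀.₉₇₅ + t₀.₈₀)² × [S²(1 − rm²)/m + T²(1 − rg²)] × 2/g.

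The t sum is 2.074 + 0.858 = 2.932. The variance inputs are not in the text available to me, so the figures cannot be reproduced exactly, but they are plausible. With an assumed variance ratio of 0.02, rm = 0.5 and rg = 0.3, the bracket divided by S² is 0.025 + 0.0182 = 0.0432. The effect size is then 2.932 × √(0.0432 × 2/12) = 0.249, inside the stated 0.21 to 0.26. With 85% follow-up the factor is √[(0.025/0.85 + 0.0182)/0.0432] = 1.05, as stated.

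Implied standard errors: sitting 14.6/2.932 = 4.98 min; LPA 12.2/2.932 = 4.16 min.

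**3. Illustration at 24 months, full retention (r = 1).** Assumption: the 12-month standard error carries over to month 24, since 12.2 gives no 24-month inputs. The table shows the chance of a significant contrast (noncentral t, 22 df) by MOVE+ catch-up u.

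| Retained difference | u = 0 | 0.25 | 0.5 | 0.75 | 1 |
|---|---|---|---|---|---|
| Sitting 14.6 min | 80% | 56% | 29% | 11% | 5% |
| Sitting 20 min | 97% | 82% | 48% | 16% | 5% |
| Sitting 30 min | >99% | 99% | 82% | 30% | 5% |
| LPA 12.2 min | 80% | 56% | 29% | 11% | 5% |
| LPA 38.4 min | >99% | >99% | 99% | 60% | 5% |

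A sitting contrast below 2.074 × 4.98 = 10.3 min is non-significant. The expected contrast falls below that once u exceeds 1 − 10.3/30 = 0.66 (δ = 30) or 1 − 10.3/20 = 0.48 (δ = 20). The 30 and 38.4 min values echo the preliminary studies cited in 12.2, which are not STAND+ against MOVE+ comparisons. The 20 min value is purely an assumption.

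**4. Precision of a within-STAND+ change from month 12 to 24.** With variance constant over visits, its variance is (2/g)[S²(1 − ρm)/m + T²(1 − ρg)], where ρ is the 12-to-24-month correlation. If these correlations equal the baseline-to-12-month ones, the ratio to the planning variance is a weighted mean of 1/(1 + rm) and 1/(1 + rg), whatever the variance ratio. With 11 df, t = 2.201.

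| Correlations | Variance ratio | Sitting SE | Sitting half-width | LPA half-width |
|---|---|---|---|---|
| both 0.3 | 0.769 | 4.37 | 9.6 | 8.0 |
| both 0.8 | 0.556 | 3.71 | 8.2 | 6.8 |
| baseline-to-12 0.3, 12-to-24 0.8 | (1 − 0.8)/(1 − 0.3²) = 0.220 | 2.33 | 5.1 | 4.3 |
| baseline-to-12 0.8, 12-to-24 0.3 | (1 − 0.3)/(1 − 0.8²) = 1.944 | 6.94 | 15.3 | 12.8 |

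Half-widths are 95%, in min/8 h, before dropout. Section 12.1 says that "if on average only 85% are followed, the detectable effect sizes increase by a factor 1.05", but that factor concerns the between-arm effect, so it is not applied here.

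**The case against.** **'Similar' most naturally means the class of model.** Section 12.1 speaks of the analysis approach, and a repeated-measures model with arm-by-visit terms can yield within-arm changes. This is a fair reading. A reader might infer that the plan intends to treat a null 24-month contrast as loss of effect. No section says so. What stands is that the arm contrast is the only one described and that no maintenance quantity is named.

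**The arms did not have one identical programme.** A reader might infer that only the timing of the desk differs at month 24, and call the contrast early versus delayed desks. Section 7.3 does not support that, because goals, coaching strategies and some newsletter content differed. So δ is not a pure desk effect, and full uptake (u = 1) may be more than the month-12 provision can deliver. Partial uptake still confounds the contrast.

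**A positive contrast might be read as a firm lower bound on retention.** That also goes too far. It suggests some retention only if uptake in MOVE+ is not negative and other changes after month 12 are equal in both arms.

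**The within-arm change is not randomised.** It also reflects withdrawal of support, secular trend and dropout, and it does not estimate r. This stands. It is why the arm contrast should be kept, and why the within-arm estimate needs an explicit caveat.

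**The 24-month outcomes carry no hypothesis.** This stands too, and limits the severity.

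**Conclusion.** The point holds for the 24-month maintenance analysis and should be fixed. As written, 12.1 leads to a contrast that cannot distinguish complete retention with complete uptake from complete loss with no uptake, and it offers no alternative. The non-identification follows from the design, given equal other changes in both arms. The probabilities in the working also depend on the assumed δ, full retention and the carried-over standard error, and serve only as illustration.

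The 3-month contrast is unaffected, because the arms still differ then. A reader might infer that the 12-month results are weakened as well. They are not, provided the 12-month measures are taken before the MOVE+ desks are installed. No figure in 12.2 is shown to be wrong.

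**What to change.** In 12.1, keep the between-arm contrast for 3 months. For 24 months, write in:

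1. **Within-STAND+ change from month 12 to month 24**, from the same hierarchical model with arm-by-visit terms and a worksite-based confidence interval, as the estimate of whether STAND+ levels held. Interpret it by the loss in min/8 h that the interval rules out, not by a non-significant decline. State that it is non-randomised and also reflects support withdrawal, secular trend and dropout. If planned precision is quoted, give both ranges with their conditions: for sitting, 8.2 to 9.6 min/8 h if the two correlations are equal within 0.3 to 0.8, and 5.1 to 15.3 if they differ; for LPA, 6.8 to 8.0 and 4.3 to 12.8.
2. **MOVE+ change from month 12 to month 24**, reported as a before-after estimate.
3. **The 24-month arm contrast**, kept as the randomised comparison and labelled: desks from the start with standing-targeted support versus desks added at month 12. State that a null is not evidence of lost effect, and give the two conditions under which a positive value suggests some retention.

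Also state that the 12-month measures precede installation in MOVE+.

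The cost is plan wording and additional contrasts from one model. No new data are needed and desk provision does not change. The drawback is that the leading estimate of whether levels held is non-randomised and has to be reported as such.

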
### 12.2 Power Analysis

We aim to enroll 24 worksites ( $N=12$  per condition) evenly distributed across Arizona and Minnesota with on average 30 employees per worksite (Total N members = 720 employees). In a baseline-adjusted analysis, let D represent the minimal detectable intervention effect, g the number of worksites per experimental condition, m the average number of members per worksite,  $S_2$  the member variance,  $T_2$  the work-site level variance,  $r_m$  and  $r_g$  the member and work-site correlations over time respectively, and  $t(d, a/2)$  and  $t(d, p)$  the critical t-statistic values based on d df for  $a/2$ =Type I alpha level (2-sided) and  $p$ =power. Then the minimal detectable difference is  $D_2 = (t(d, a/2) + t(d, p))^2 (S_2(1 - r_{2m})/m + T_2(1 - r_{2g}))^2 / g$ . Dividing by  $S_2$  yields the square of the Effect Size (ES) and  $T_2/S_2$  is the variance components ratio (VCR). In the unlikely

situation where the  $g$  are unequal, replacing  $2/g$  by  $(1/g_0+1/g_1)$  will lead to a minimal increase in  $D$  unless the  $g$  are grossly unequal. With  $g=12$  (worksites per condition),  $d=22$ , and  $N=720$ ,  $m=30$ ;  $\alpha/2$  is set to 0.025 and power is set 80%. The detectable effect sizes for this trial range from 0.21 to 0.26 across the three outcomes, which are relatively small effects, and thus we are well powered in this study. On an absolute scale, as also shown in the table, we will be able to detect a difference between intervention arms as small as 12.2 min/8-hr work day of LPA and 14.6 min/8-hr work day of sitting time. Our preliminary studies clearly demonstrate our ability to achieve these effects: (a) For LPA; the crossover study (12) showed a 38.4min/8-hr workday increase (other two studies did not target LPA or did not use a monitor designed to detect LPA); (b) for sitting, both the crossover and natural experiment showed >30min/8-hr workday reductions; and (c) for cardiometabolic risk, all 3 studies showed moderate to large effect sizes. This study is powered well to detect effects that are considerably smaller than what we have observed in our preliminary studies

## 12. Adverse Event Reporting and Recording

Adverse events will be monitored during the study to ensure timely detection of events that may affect safety or continued participation. Protocol defined adverse events, as well as any unanticipated adverse events deemed possibly or probably related to study procedure, must be immediately reported to the study PI and/or Project Coordinator. In the event an adverse event occurs, the PI will submit an adverse event report to the IRB within 24hrs.

## Appendix 1. ActivPAL processes

### Appendix 1.1 ActivPAL Waterproofing and Taping

1. Wrap a finger cot around an initialized activPAL.

[figure not shown]

2. On the finger cot, label the activPAL with participant's ID number and an arrow going up (in the same direction as the human body on the activPAL). Ensuring orange side up, as pictured.
3. Wrap a 12cm by  $\frac{1}{2}$  of the width of the wide opsite (clear) tape around the activPAL. Make sure the activPAL is thoroughly covered. This can be done efficiently by sticking one end of the opsite tape onto the edge of a table and rolling the activPAL up the length of the tape.
4. Cut out a 6 by 6 cm piece of hypafix (white) tape and a 6 by 6 cm piece of opsite tape.
5. Place the waterproofed activPAL in the center of the white side of the hypafix tape.
6. Place the opsite tape over the activPAL to secure it to the white side of the hypafix tape.
7. Use extra small opsite pieces of tape to ensure that the activPAL is secured to the hypafix tape. The activPAL should look like this:
8. Do not peel off the back of the hypafix tape until it is time to place it on the participant's leg.

[figure not shown]
### Appendix 1.2. Initialization

[figure not shown]
1. To initialize, place your designated activPAL into the 'PC INTERFACE' port; the other ports only serve as a charging area.
2. Plug in the activPAL dock to the computer/laptop using a micro USB cord.
3. Open the activPAL software and select File, then 'Connect to ActivPAL'

4. Verify Battery Level is at least **4.15 Volts**
5. Next select Setup – this is for initializing devices only.

6. Select '**Future Time**,' Enter in your participants de-identified 5 digit ID in the **recording identifier** section; choose your starting time (Stand and move is always **10:00 am**); Choose your starting date; then select record for **14 days**. Then hit program.

7. Click OK.
8. Remove the device.

### Appendix 1.3. Handout instructions for reaffixing activPAL

#### To reaffix your activPAL:

If your activPAL is loose, or falls off, use the hypafix tape provided in your activPAL pack to reaffix the device to your right thigh.

We will also leave extra tape at your worksite in case you need more.

Remember that when affixing your activPAL, the arrow needs to be facing outwards and be pointing up.

[figure not shown]
If you need additional tape please email us at [[contact]](mailto:[contact])

[figure not shown]
### Appendix 1.4. Data download and processing.

1. Load activPAL software. Double click Icon on Desktop.
2. Insert ActivPAL into dedicated port on dock labeled 'PC INTERFACE'. Then, connect dock to desktop tower via USB cable.
3. Select 'File' --> 'Connect to ActivPAL'
4. Select 'Download' from top left of the 'PALconnect' window (unless download screen opens first)
5. Verify Identifier to participant # in Database.
6. Click 'Download Stored Data'
7. To save recording data, Click New Folder
8. Select the appropriate folder. E.g., for Stand&move@work: X:\[name] Lab\Stand and Move ASU\_UMN\Data\ActivPAL\Visit #\ParticipantID#; (Visit= T1, T2, T3, T4, etc. based on timeline for each site); Participant ID= 5 digit number as indicated in Participant Database
9. Check the folder where you saved the data to double check that the file has been correctly downloaded. (6 files uploaded for each participant).
10. Once the data has been successfully downloaded, select view at the top of the activPAL software screen. Then select "view by week," and open the corresponding pal file. This is what we will be sharing with participants as feedback. In order for the activPAL data to be considered valid, there needs to be four valid days with 8hour/day of valid wear time per day.

